4.2 What are the planned trial interventions?

Standard arthroscopic repair of the rotator cuff tear will take place. Ten to 14 days prior to the repair, one of two techniques for preparation of the cuff insertion site will be used; either bone trephination or soft tissue trephination.

Ten to 14 days following the experimental procedure, the cuff repair operation will be carried out with standard technique. The two surgeons in the trial have adopted a standardized approach to arthroscopic cuff repair. Prophylactic antibiotics will be administered with either cefazolin or in the case of penicillin allergy, Clindamycin. An examination under anesthesia will be performed and documented. All will undergo a standard diagnostic arthroscopy. All shoulder pathology encountered will be documented on a standardized form. The surgical repair will proceed using standard arthroscopic technique. Peek suture anchors will be used to carry out the repair. The number of anchors used is at the discretion of the surgeon, and will be based on the size and complexity of the tear. Duration of the surgery will be between 60-120 minutes.

Preoperative site preparation: Bone Trephination or Soft Tissue Trephination

Both pre-operative procedures will be performed under local anesthesia. A mixture of lidocaine (5 mL, 2% and Marcaine 5 mL, 0.5%) will be injected into the subacromial space under sterile technique. The skin site will also be infiltrated.

After the local anesthetic is infiltrated, a 14 gauge core biopsy needle will be introduced percutaneously and under ultrasound guidance to the exposed area of the cuff insertion site. For the bone trephination, the needle will be advanced into the insertion site through the cortex and into the metaphyseal bone of proximal humerus. This procedure will be repeated such that a grid pattern of 4 holes in the insertion site will be created in a rectangular pattern.

The soft tissue trephination will be carried out in a similar fashion with percutaneous introduction of the needle. The needle will be advanced through the rotator cuff tissue stump at the insertion site but will not be advanced through the cortical bone. This procedure will be carried out in a grid pattern with 4 holes through the soft tissue created in a rectangular pattern.

An arthroscope will be used in both the soft tissue and bone trephination procedures, to further assist in guiding the needle to the precise location during the trephination procedure.

A 14 gauge needle was chosen for the trephination technique as this is large enough to create a tunnel through soft tissue or bone, can be used manually and does not require the use of power equipment, is small enough to allow for 4 trephination points without weakening the bone of the greater tuberosity but large enough to allow for bleeding and communication with the marrow. Such needles are typically used for core biopsy of tumours localized in bone. Ultrasound was chosen to guide the needle to the insertion site as this is a simple and cost effective method to provide needle localization. Its use has been well-established for use for needle localization in other disciplines.(43) The depth of the needle for bone trephination will be established by direct measurement on plain shoulder xrays.

If patients are interested in enrolling in the study, but are not willing to consent to an adjuvant procedure, patients will be offered the option of undergoing the trephination procedure at the time of the cuff repair. In this case, the intervention would be as follows:

Standard arthroscopic repair of the rotator cuff tear will take place. Immediately prior to tendon repair, one of two techniques for preparation of the cuff insertion site will be used; either bone trephination or soft tissue trephination.

The cuff repair operation will be carried out with standard technique. The two surgeons in the trial have adopted a standardized approach to arthroscopic cuff repair. Prophylactic antibiotics will be administered with either cefazolin or in the case of penicillin allergy, Clindamycin. An examination under anesthesia will be performed and documented. All patients will undergo a standard diagnostic arthroscopy. All shoulder pathology encountered will be documented on a standardized form. The surgical repair will proceed using standard arthroscopic technique. Peek suture anchors will be used to carry out the repair. The number of anchors used is at the discretion of the surgeon, and will be based on the size and complexity of the tear. Duration of the surgery will be between 60-120 minutes.

Preoperative site preparation: Bone Trephination or Soft Tissue Trephination

As part of the surgical preparation of the tendon insertion site, a 2 mm K-wire will be introduced under direct arthroscopic visualization to the exposed area of the cuff insertion site. For the bone trephination, the wire will be advanced into the insertion site through the cortex and into the metaphyseal bone of proximal humerus. This procedure will be repeated such that a grid pattern of 4 holes in the insertion site will be created in a rectangular pattern.

The soft tissue trephination will be carried out in a similar fashion. The wire will be advanced through the rotator cuff tissue stump at the insertion site but will not be advanced through the cortical bone. This procedure will be carried out in a grid pattern with 4 holes through the soft tissue created in a rectangular pattern.

A 2mm K wire was chosen for the trephination technique as this is large enough to create a tunnel through soft tissue or bone, is small enough to allow for 4 trephination points without weakening the bone of the greater tuberosity but large enough to allow for bleeding and communication with the marrow. The depth of the needle for bone trephination will be established by direct measurement on plain shoulder xrays.

Post-operative Care and Physiotherapy

All procedures will be carried out on an out-patient basis. Post-operative care will be identical in both groups and occur with close guidance from their physiotherapist.

Following repair of the rotator cuff, early passive motion of the shoulder is initiated. Both passive forward flexion and external rotation are implemented, as are passive pendular motions. The rehabilitation protocol will occur as follows:

- ◆ 0 to 6 weeks: pendulum exercises with progression to passive (assisted) exercise. A sling is worn for the first 4-6 weeks for protection.
- ◆ 6 -12 weeks: stretching and continuation of active-assisted exercise, including forward elevation and external rotation. Patients will be encouraged to begin gentle use of the shoulder (brushing teeth, combing hair etc).
- ◆ after 12 weeks: active/resistive exercise will be undertaken. Full use of the arm will be allowed. Restrictions will include heavy lifting below shoulder level, and lifting above shoulder level.
- ◆ After 6 months: no further restriction will be placed. Full home and work activity allowed.

4.3 Proposed practical arrangements for allocating participants to trial

A treatment allocation schedule will be produced under the supervision of the orthopedic research study coordinator. Allocation to either bone trephination or soft tissue trephination will occur in blocks of 10 in a randomized fashion. Treatment allocation will be determined when the patient is scheduled for surgery. Treatment allocation will be stratified by surgeon.

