4.1 THE PROPOSED TRIAL

What is the proposed trial design?

Single center, randomized controlled trial.

Recruitment: Up to 180 consecutive men and women, aged 18 or older with surgical indication for surgical repair of a full-thickness rotator cuff tear consulting one of two Ottawa shoulder surgeons ([name] or [name]). Both surgeons have extensive experience with arthroscopic cuff repair, and are both shoulder fellowship-trained subspecialists. When meeting inclusion and exclusion criteria and providing informed consent, they will be included in this randomized controlled trial. Up to 90 patients will be randomized in blocks of 10 consecutive patients to either a bone trephination group or a soft tissue trephination group. Treatment allocation will be stratified by surgeon. We require a sample size of 90 participants who have been randomized *and* received the intervention, and thus we will need to recruit up to 180 participants, as we have experienced a high percentage (~50%) of participants who were lost to follow up or excluded prior to randomization (reasons include cancelling surgery, not being available for the pre-operative trephination and withdrawing consent).

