4.4 What are the proposed methods for protecting against sources of bias?

Blinding: Due to the nature of a surgical trial, the surgeon may not be blinded to the intervention. However, a trained MSK radiologist will carry out the post-operative imaging, both ultrasound and MRI, and will be blinded to the nature of the treatment. Further, an independent assessor will carry out the follow-up functional assessments and will be blinded. This will minimize the potential for biases introduced by the examiner when performing the physical assessment and recording data. The assessor will not have access to the patient chart prior to the examination. The patient will also be blinded to the treatment assignment. To help reduce the potential for observer bias, the physical examination and the administration of study questionnaires are standardized.

Control of contamination and co-intervention:

Co-interventions will be documented. These are to include physiotherapy including the number of sessions and the nature of the physiotherapy intervention. The type and frequency of pharmaceutical agents used by the patient post-operatively will also be documented. In addition, all intraoperative adjunctive procedures will be documented, as well as details of the treatment method and implants used.

Ensuring complete follow-up: The following measures will help to ensure completion of follow-up: a) study patients will supply their own address, telephone, and email information, and the name, relationship, address, telephone, and email information of someone who does not reside with the patient, but is likely to have contact with them should they move or change telephone information, b) patients will receive a copy of the consent form which will outline the purpose of the study, the importance of their individual participation and attendance for follow-up assessments, and c) the research coordinator will maintain regular contact with the patients.

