4.9 How will the outcome measures be measured at follow-up?

The collection and administration of all outcomes and examinations are standardized and are clearly outlined in the Study Protocol Manual. Surgeons and research assistants will have met on several occasions to discuss and review this protocol.

PRIMARY:

The patients will complete the WORC Score questionnaire pre-operatively and at 3, 6, 12 and 24 months post-operatively. The research assistant, blinded to treatment allocation, will be available to answer any questions. The patient will be examined by the blinded research assistant in a standardized fashion. The surgeon is the last person to examine the patient.

SECONDARY:

The patients will complete the ASES and Constant Score questionnaire pre-operatively and at 3, 6 12 and 24 months post-operatively. The research assistant will be available to answer any questions. The patient will be examined by a blinded assessor in a standardized fashion. The surgeon is the last person to examine the patient and is blinded to the results of the outcomes.

The interpretation of the high-resolution ultrasound is based on healing status and will be carried out by a trained MSK radiologist. Healing status will be documented at both 6 and 24 months as either completely healed, partially healed, or not healed. For tendons partially healed or not healed, the size of the defect will be compared with the size of the tear pre-operatively.

The quantitative T1-MRI will be interpreted by a trained MSK radiologist.

Analysis of the healing matrix will be carried out as described above.

4.10 What is the proposed sample size and what is the justification for the assumptions underlying the power calculations?

The sample size calculation was based on a scale score of 71.31 and standard deviation of 30.43. The authors are assuming superiority from historical controls. Superiority would be considered a difference of more than 30%, or 21.4 points on the WORC scale, from the expected mean. With alpha at 0.05 and power 0.80, the sample size was determined at 33 per group. With a foreseen dropout rate of 25%, we would therefore seek 45 patients per group.

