We have experienced a much higher than anticipated rate of withdrawal (~50%) which has mainly been due to 'loss to follow up', or being excluded at the time of surgery, in particular, there has been a large number of participants who signed the consent and completed baseline measures, but never booked a surgery, were not available for the pre-operative trephination procedure, or withdrew consent prior to randomization. Given that we require a sample size of 90 participants who have been randomized *and* received the intervention, we would like to recruit up to 180 participants, however, recruitment will be ceased once 90 participants have been randomized and received the pre-operative intervention.

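### One disclosed block size of 10 within surgeon, with no allocation concealment described, could let an enrolling surgeon foresee up to about 15–17% of allocations

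*Combined protocol and SAP*

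**What the plan says.** - **Block size and strata.** Section 4.3 states that allocation "will occur in blocks of 10 in a randomized fashion" and that "Treatment allocation will be stratified by surgeon". Section 4.1 has "Up to 90 patients will be randomized in blocks of 10 consecutive patients". No other size and no variation in size is mentioned.
- **Ratio.** Section 4.10 gives "we would therefore seek 45 patients per group", which implies 1:1 allocation.
- **Timing.** Section 4.3: "Treatment allocation will be determined when the patient is scheduled for surgery".
- **Who does what.** The schedule is produced under the study coordinator's supervision (4.3), and the coordinator implements randomization (trial management section). The two surgeons enrol the patients (4.11).
- **Blinding.** Section 4.4 accepts that "the surgeon may not be blinded to the intervention". Its protections are a blinded radiologist, assessor and patient, and standardised assessment.
- **Stopping recruitment.** Section 4.10: "recruitment will be ceased once 90 participants have been randomized and received the pre-operative intervention".

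The protocol does not describe central or web release, sealed envelopes, or withholding of the block size. It also does not say who books surgery, who performs the separate pre-operative trephination, or when a surgeon learns each patient's arm.

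**The concern.** Within a balanced block of known size, once one arm is used up every remaining allocation in the block is known. Each stratum here is a single surgeon's caseload, so only one sequence has to be followed. In the same-session option of section 4.2 the trephination is done under arthroscopic view during the repair, so the operator sees the arm.

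Several eligibility criteria in 4.5 call for judgement, such as benefit from repair, significance of comorbidity and physiologic age. The scheduling date can also be moved. A surgeon who foresees the next arm could bring a patient forward, defer or exclude on prognosis. That would unbalance the arms before treatment, and the blinded outcome assessment in 4.4 cannot undo it. At stake is the bone versus soft-tissue comparison of 24-month WORC posed in the section 4 research question and null hypothesis.

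**Working it through.** The plan gives no figure for predictability, so there is none to reproduce. Its 33 per group (4.10; difference 21.4, SD 30.43, two-sided 5%) does reproduce: noncentral-t power is 0.791 at 32 and 0.803 at 33. It is used below only for scale, in step 6.

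**Inputs.** Block size 10 (4.1, 4.3); two surgeon strata (4.1, 4.3); 90 randomized (4.1); 5:5 within each block (assumption, following from 45 per group in 4.10). The split of 90 between surgeons is not given, so two splits are shown.

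**1. Certain allocations in a complete block.** There are C(10,5) = 252 equally likely arrangements. After k allocations, one arm is used up with probability 2·C(k,5)/252, and allocation k+1 is then certain.
- 6th: 2/252 = 0.8%
- 7th: 12/252 = 4.8%
- 8th: 42/252 = 16.7%
- 9th: 112/252 = 44.4%
- 10th: 252/252 = 100%

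The sum is 420/252 = 1.667 per block, or 16.7%. The closed form agrees: 2m/(m+1) with m = 5 is 10/6.

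**2. Over 90 patients.**
- Split 40/50: nine complete blocks, 9 × 1.667 = 15.0 (16.7%).
- Split 45/45: four complete blocks per surgeon plus the first five places of a fifth, none of which is certain. 2 × 4 × 1.667 = 13.3 (14.8%).

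**3. If the surgeon is behind.** If the latest L allocations are unseen, the last L terms of the sum in step 1 drop out. For nine complete blocks:
- L = 1: 168/252 = 0.667 per block, 6.7%, about 6 of 90
- L = 2: 56/252 = 0.222, 2.2%, about 2 of 90
- L = 3: 14/252 = 0.056, 0.6%, about 0.5 of 90

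Section 4.11 plans 60 patients a year. Split equally, that is 30 per surgeon, or one every 365/30 ≈ 12 days. The interval between scheduling and the surgeon learning the arm is not given, so the documents do not settle which L applies.

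**4. Best guess.** Always guessing the arm with more places left gives 5 + (1024/252 − 1)/2 = 6.53 correct of 10 (65.3%), against 50% by chance.

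**5. Alternatives.** For a fixed size 2m the certain share is 1/(m+1): size 8 gives 20%, size 6 gives 25%, size 4 gives 33%. Random sizes were simulated in sequences of 45, for an observer who knows all earlier allocations and the set of sizes:
- fixed 10: 14.7% certain (agreeing with 14.8% in step 2), best guess 64%
- 6, 8 and 10: 1.7% certain, best guess 66%
- 4, 6 and 8: 2.4% certain, best guess 67%

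**6. Scale of bias (illustration only).** Assume that steering on certain allocations makes prognosis differ between arms by 10 WORC points. This figure is not in the documents, and the result scales in proportion to it. Bias = share certain × 10.
- fixed 10, all earlier allocations known: 1.5 to 1.7 points
- fixed 10, latest one unseen: 0.7
- random 6, 8 and 10: 0.2

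The standard error of the difference at 33 per group is 30.43 × √(2/33) = 7.5 points, and the target difference is 21.4.

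**The case against.** The case against is substantial, and much of it stands.

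- **Who controls the sequence.** A reader might infer that the surgeons book the patients and carry out every trephination, and so see their whole sequence. The documents say neither. They say that surgeons enrol and that the coordinator implements randomization, and section 4.2 names no operator for the separate pre-operative procedure. The route to bias is therefore enrolment by a surgeon who may be unblinded.
- **One in six as a consequence.** It is tempting to read 16.7% as what the design produces. It needs knowledge of every earlier allocation in the stratum. Both arms have the same kind of procedure visit, so a booking need not reveal the arm.
- **Block size as the main fault.** Ten is less predictable than any smaller fixed block, and random sizes do not lower the best-guess rate. The larger gap is the absence of a concealment step.
- **The roughly 50% loss.** A reader might take this as a sign of steering. Section 4.1 places it before randomization and gives ordinary reasons for it. Only the exclusions at surgery mentioned in 4.10 could follow allocation, and block size does not affect those.
- **The primary analysis.** Section 4.14 compares WORC with database controls who had no trephination. That comparison does not rest on random allocation between the arms, so foreseeing the next arm is not what threatens it.
- **Size.** Even with an assumed 10-point steer, the bias is about 0.2 standard errors (1.7/7.5).

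What the objection does not remove is that the protocol discloses the one number needed to track a block and states nothing that would stop an enrolling surgeon from doing so.

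**Conclusion.** The point holds as a cheap improvement. A single disclosed block size within surgeon, enrolment by surgeons who may be unblinded, and no described concealment together leave the randomized bone versus soft-tissue WORC comparison open to selection bias. Foreseeable allocations number at most 13 to 15 of 90 (15–17%), and under 1% if surgeons run three allocations behind. The range rests on 5:5 blocks and on when surgeons learn the arm, which the protocol leaves open. Nothing in the documents shows that any allocation has been steered.

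**What to change.** For patients not yet allocated:

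1. In 4.1 and 4.3, replace the fixed size with 1:1 permuted blocks of randomly varying size within surgeon. Hold the sizes (for example a mix of 6, 8 and 10) in a document that the surgeons cannot see.
2. State in 4.3 that the coordinator releases each allocation only once pre-operative eligibility and baseline WORC are recorded and the patient is irrevocably enrolled. Eligibility has to be limited to pre-operative criteria, because 4.5 also requires intra-operative confirmation of the tear. Section 4.10 mentions participants who completed baseline measures but never booked surgery, so recording baseline first should change little in practice.
3. Reword "randomized in blocks of 10 consecutive patients to either a bone trephination group or a soft tissue trephination group" in 4.1, which can be read as giving a whole block one treatment.

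Step 1 alone is not enough. It cuts certain allocations to about 2% even if the set of sizes is known, but the best-guess rate stays near 65%, so undisclosed sizes and concealed release are essential parts of the change.

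The cost is a short amendment and a regenerated list. With a largest block of 10, the maximum imbalance per surgeon remains 5, as now. Recruitment was already under way at this version (4.10), so the gain is limited to allocations still to be made.

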4.4 What are the proposed methods for protecting against sources of bias?

Blinding: Due to the nature of a surgical trial, the surgeon may not be blinded to the intervention. However, a trained MSK radiologist will carry out the post-operative imaging, both ultrasound and MRI, and will be blinded to the nature of the treatment. Further, an independent assessor will carry out the follow-up functional assessments and will be blinded. This will minimize the potential for biases introduced by the examiner when performing the physical assessment and recording data. The assessor will not have access to the patient chart prior to the examination. The patient will also be blinded to the treatment assignment. To help reduce the potential for observer bias, the physical examination and the administration of study questionnaires are standardized.

Control of contamination and co-intervention:

Co-interventions will be documented. These are to include physiotherapy including the number of sessions and the nature of the physiotherapy intervention. The type and frequency of pharmaceutical agents used by the patient post-operatively will also be documented. In addition, all intraoperative adjunctive procedures will be documented, as well as details of the treatment method and implants used.

Ensuring complete follow-up: The following measures will help to ensure completion of follow-up: a) study patients will supply their own address, telephone, and email information, and the name, relationship, address, telephone, and email information of someone who does not reside with the patient, but is likely to have contact with them should they move or change telephone information, b) patients will receive a copy of the consent form which will outline the purpose of the study, the importance of their individual participation and attendance for follow-up assessments, and c) the research coordinator will maintain regular contact with the patients.

